#### *Enhancing the uptake of psychological therapy*

Psychosocial therapies are currently the mainstays of treatment for alcohol dependence but are of limited effectiveness, which may partly be because they depend on the brain's capacity for neuroplastic change [63]. Psychological therapies in alcoholism are also less effective in individuals with cognitive impairment [64]. Undergoing learning based psychological therapy during the period of neurogenesis and synaptogenesis, which commences around two hours after an acute dose of ketamine [53], may facilitate its uptake as the brain is primed to make new connections and learn new information. Increased synaptogenesis has been linked with improved memory [e.g. 65; 69]. Therefore ketamine may enhance the uptake of psychological therapy in the hours following an acute dose by making the brain more receptive to new learning.

The notion that treatments that stimulate neurogenesis and synaptogenesis in this manner may work synergistically with psychological therapies is becoming more accepted [90] and may represent a future paradigm shift in the treatment of mental health problems. Historically, approaches to treating alcoholism that involve psychological therapy and provoke neurogenesis have enjoyed some success [see e.g. 91 for a review] but it is only recently that the biological mechanisms have been elucidated. In order to examine whether enhancing the uptake of therapy is the mechanism by which ketamine is effective in alcoholism we have included a ketamine + 'no therapy' arm in the trial. These data will have considerable implications not only for alcohol dependence, but also

depression as this may suggest a similar psychotherapy plus ketamine approach may enhance the effectiveness of ketamine treatment.

*Additional advantages of ketamine: glutamatergic actions*

Ketamine also acts as an antagonist of the glutamatergic N-methyl-d-aspartate receptor. Glutamatergic activation and glutamate receptor up-regulation contribute to alcohol dependence and withdrawal [66]. Acute detoxification is associated with a hyperglutamatergic effect that NMDA-receptor antagonists have been shown to normalise [66]. Excess glutamate is known to have toxic effects, and ketamine may protect against some of these adverse effects.

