## 7.2 Randomisation procedures

A blocked design for randomisation will be used to allocate patients using a 1:1:1:1 ratio for the 4 respective groups. Randomisation will be performed by a specialist company ([www.sealedenvelope.com](http://www.sealedenvelope.com)) who will hold the randomisation list and provide 24/7 internet access for unblinding services. Early drop-outs (during screening and the baseline week up until randomisation) will be replaced. Once patients have been randomised at week 0 they will not be replaced regardless of compliance or dropout status and will be analysed as part of the intention to treat analysis. After randomisation, the site research team will be given a unique trial randomisation code via email from [sealedenvelope.com](http://sealedenvelope.com). This code corresponds to an envelope at the site which contains the treatment allocation. These envelopes will be provided by the trial statistician at the start of the trial and are kept in a secure location by allocated partially unblinded staff. The trial statistician will be provided the treatment allocation codes prior to the start of the trial to prepare the envelopes. Separate envelopes will be provided for the delegated staff preparing the IMP (containing the IMP treatment allocation) and the psychology staff (containing the psychological treatment allocation). To protect the blind, pharmacy or delegated unblinded staff preparing the IMP at site will be notified separately via email of the randomisation code. An additional email is sent to the psychology team at site who can refer to the correct envelope to determine the psychological treatment allocation. Randomisation details of patients will be entered on a trial Subject Log and will follow the instructions set out in a Standard Operating Procedure (SOP) on randomisation. Data review will take place when half the target samples have been randomised. Upon randomisation, patients will be given a study specific patient card which will have study title, IMP details, patient ID and contact details of the out of hours contact in cases of emergency.

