### **13.3.2 Primary outcome analysis**

There are two primary outcomes: (i) proportion relapsed (recommenced using alcohol) at 6-month follow-up; and (ii) percentage of days abstinent at 6-month follow-up (the denominator being 175 days). The proportion of relapsed participants at 6-month follow-up will be reported as a percentage for each arm, as well as for the ketamine arms combined and

the psychotherapy arms combined. Although no formal power calculations for a between-group analysis have been performed, the proportion of relapsed participants at 6-month follow-up will be expressed as a relative risk (RR) with a 95% confidence interval for the following comparisons: (i) all ketamine participants versus all non-ketamine participants; (ii) ketamine + psychotherapy participants versus ketamine + non-psychotherapy participants; and (iii) ketamine + psychotherapy participants vs. placebo + no psychotherapy participants. These analyses are purely exploratory and should be viewed with caution both in the light of lack of power and multiple testing. Percentage of days abstinent at 6-month follow-up will be reported descriptively in the same way by arm and combination of arms; additionally, the between-group mean differences and 95% confidence intervals will be reported for the comparisons set out above; again, these analyses should be regarded as exploratory. The primary analysis will be an intention-to-treat (ITT) complete case analysis including all randomised participants. A secondary analysis will be conducted including only those participants deemed to have completed to a sufficient degree their allocated interventions, that is, a per protocol analysis. All analyses will be performed by a statistician who is blinded to the treatment allocations and will be performed using Stata v.13.

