4.4 Study design

KARE has two interventions (drug therapy and psychological therapy), each with two possible forms, resulting in a two by two factorial intervention design, with a total of four possible interventions (Section 4.1).

The drug intervention will be administered by the site anaesthetist, who will be blinded to drug allocation and psychotherapy allocation. Psychotherapy/psychoeducation will be administered by the trial psychologists at each site who will be blinded to the drug allocation. Participants will also be blinded to drug allocation. Participant outcome data will be collected by site investigators who are blinded to drug allocation. The trial statistician will be blinded to both drug allocation and psychotherapy allocation throughout the trial.

Participants will be randomised to the trial after eligibility has been confirmed via prescreening and screening, and after having provided informed consent. The SCRAM-X ankle monitor (measuring alcohol levels in sweat) will be attached at screening. Treatment will commence as soon as possible after randomisation, and continue for a period of 3 weeks (one infusion session and two sessions of psychological therapy/psychoeducation per week). Follow-up data will be collected at 3 and 6 months after baseline. The last follow-up visit is scheduled for 24 weeks post baseline.

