4.5 Purpose of the analyses

The purposes of the analyses are as follows:

- (i) to provide baseline descriptive data by trial arm;
- (ii) to assess the feasibility of data collection;
- (iii) to assess loss to follow-up at 3 and 6 months;

- (iv) to assess the proportion of missing data at 6 months;
- (v) to provide descriptive outcome data by trial arm (ketamine vs placebo, psychotherapy vs psychoeducation, and all four arms individually) at 6 months;
- (vi) to provide relative risks (with 95% confidence intervals) for relapse of alcohol consumption comparing (a) ketamine vs placebo; (b) ketamine plus psychotherapy vs ketamine plus psychoeducation; (c) ketamine plus psychotherapy vs placebo plus psychoeducation;
- (vii) to provide mean difference (with 95% confidence intervals) for percentage of days abstinent at 6-month follow-up for the same combinations by arm as for (vi); and
- (viii) to descriptively report adverse events.

All inferential analyses are to be regarded as exploratory and viewed with caution due to lack of statistical power and multiple testing. For the primary outcomes, the primary analyses will be performed on an intention to treat (ITT) basis using complete case data only (see Section 6.5 for approaches to missing primary outcome data). As a sensitivity analysis, the inferential analyses for the primary outcomes only (vi and vii above) will be performed using only those participants deemed to have completed their allocated interventions to a specified degree (per protocol analysis). For the participants who receive ketamine, a per protocol treatment will be defined as receiving three or more infusions. No specification of a minimum treatment has been defined for psychotherapy/psychoeducation. Hence, all participants who receive placebo drug therapy will be considered as having been treated per protocol. For the secondary outcomes, only an ITT analysis using complete case data will be performed. All analyses will be performed by a statistician who is blinded to treatment allocation. All analyses will be performed using Stata v14.

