6.3 Covariates and subgroups

All inferential analyses will be adjusted by site. Due to the small number of participants, and the feasibility nature of the study, no subgroup investigations will be performed.

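### The protocol includes a ketamine-without-therapy arm to examine whether ketamine enhances therapy, but no planned contrast estimates the drug-by-therapy interaction

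*Protocol*

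**What the plan says.** Protocol section 2.4, under the heading on enhancing the uptake of psychological therapy, gives the reason for having a ketamine group without therapy, namely to find out whether "enhancing the uptake of therapy is the mechanism by which ketamine is effective in alcoholism".

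SAP 4.4 describes two interventions with two forms each, "resulting in a two by two factorial intervention design". Protocol 7.2 will "allocate patients using a 1:1:1:1 ratio for the 4 respective groups".

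Protocol 13.3.2 names three comparisons for the primary outcomes. The first two are "i) all ketamine participants versus all non-ketamine participants; (ii) ketamine + psychotherapy participants versus ketamine + non-psychotherapy participants". The third and last is "iii) ketamine + psychotherapy participants vs. placebo + no psychotherapy participants". SAP 4.5 lists the same three, "a) ketamine vs placebo; (b) ketamine plus psychotherapy vs ketamine plus psychoeducation; (c) ketamine plus psychotherapy vs placebo plus psychoeducation", and SAP 6.2 repeats them. They are called (a), (b) and (c) below. Relapse is summarised by relative risks and percentage days abstinent by mean differences, each with a 95% interval. SAP 6.4 reports no p-values.

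On covariates, SAP 6.3 says "All inferential analyses will be adjusted by site"; no other covariate is named and subgroup investigations are excluded. All four cells and both margins are reported descriptively (SAP 4.5(v), Tables 4 to 6). Both documents call the inferential analyses exploratory and underpowered.

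**The concern.** If ketamine makes the patient more receptive to therapy, the benefit of psychotherapy over psychoeducation should be larger on ketamine than on placebo. Contrast (b) measures only the ketamine half of that comparison. If therapy works equally well with and without ketamine, (b) still favours the combination. Contrast (c) changes drug and therapy together, so it mixes the drug effect, the therapy effect and any interaction. Contrast (a) averages over therapy.

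The placebo plus psychotherapy arm, which would separate ordinary therapy benefit from enhancement, is already being randomised. Without the interaction and its interval, a favourable (b) could be taken as support for the mechanism in the rationale, and nothing in the planned output would show how little the data say about it.

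A smaller point concerns (a). Its model holds site but not the other randomised factor. Balance on therapy is assured by design at randomisation, not among completers.

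**Working it through.** **Inputs.** Relapse 50% on placebo and 25% on ketamine; 24 randomised per cell, or 12 per cell after the 50% drop-out allowance (Protocol 13.2.1, SAP 4.6). The documents give no rates by therapy, so the cell rates below are assumptions that keep the 25% and 50% margins.

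**The plan's own figure.** With 24 per drug arm, the 90% interval for the 25-point difference is 0.25 ± 1.645 × √(0.5×0.5/24 + 0.25×0.75/24) = 2.8% to 47.2%. This reproduces the protocol's 3% to 47%.

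**What the contrasts can distinguish.** PT is psychotherapy, PE psychoeducation, K ketamine, P placebo.

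| | K+PT | K+PE | P+PT | P+PE | RR (a) | RR (b) | RR (c) | Therapy RR on placebo | Ratio of therapy RRs |
|---|---|---|---|---|---|---|---|---|---|
| Scenario A | 20% | 30% | 40% | 60% | 0.50 | 0.67 | 0.33 | 0.67 | 1.00 |
| Scenario B | 20% | 30% | 50% | 50% | 0.50 | 0.67 | 0.40 | 1.00 | 0.67 |

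On the relative-risk scale there is no enhancement in A, while in B therapy works only with ketamine. Contrasts (a) and (b) are identical in the two. Contrast (c) differs, but alone it cannot be attributed to drug, therapy or interaction.

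**Scale.** In A the additive interaction is (20 − 30) − (40 − 60) = +10 points, which looks like antagonism, although the ratio of relative risks is 1.00. In B it is (20 − 30) − (50 − 50) = −10 points. The two scales can disagree, so the scale must be fixed in advance.

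**Recovering it from the plan.** On the difference scale with equal cells, interaction = 2(a) + 2(b) − 2(c). In A: 2(−25) + 2(−10) − 2(−40) = +10. The point estimate is therefore recoverable, but no interval for it is planned.

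**Precision**, assuming 25% in both ketamine cells and 50% in both placebo cells, with n per cell:

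| 95% half-width, risk difference | Formula | n = 24 | n = 12 |
|---|---|---|---|
| Contrast (a) | 1.96 × √[(0.1875 + 0.25)/(2n)] | 18.7 points | 26.5 points |
| Contrast (b) | 1.96 × √[2(0.1875)/n] | 24.5 points | 34.6 points |
| Interaction | 1.96 × √[(2(0.1875) + 2(0.25))/n] | 37.4 points | 52.9 points |

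For the ratio of relative risks, the log variance is the sum of (1 − p)/(np) over the four cells, which is 8/n here. The 95% limits are the estimate multiplied and divided by exp(1.96 × √(8/n)) = 3.1 at n = 24 and 5.0 at n = 12. A 25-point interaction would have about 26% power at 24 per cell and 15% at 12 (two-sided 5%). For 80% power it needs 7.85 × 0.875/0.25² ≈ 110 evaluable per cell. No standard deviation is given for percentage days abstinent, so no width is computed for it.

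**Therapy factor in (a).** Suppose no drug effect and a 20-point therapy effect. With 12 PT and 12 PE retained in each drug arm the shift is zero. With 14/10 on ketamine and 10/14 on placebo it is 20 × (14/24 − 10/24) = 3.3 points; with 16/8 and 8/16 it is 20 × (16/24 − 8/24) = 6.7 points. Under chance loss alone, with 24 of 48 retained per drug arm, the variance of the PT share is (0.25/24) × (24/47) = 0.0053. The difference between arms then has SD √(2 × 0.0053) = 0.103, a shift of about 2 points. Simulating independent 50% retention in each cell, an imbalance as large as the 16/8 split, in either direction, occurs about 0.2% of the time.

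**The case against.** **The mechanism is a rationale, not an objective.** This is correct. Neither the protocol nor the SAP lists synergy among its objectives. Secondary objective 2 asks whether ketamine alone does as well as ketamine with psychotherapy, and (b) answers it. A reader might infer that the plan fails a stated objective; it does not. What stands is that the protocol gives this question as its reason for the arm and the analysis does not address it.

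**The information is already there.** A reader might infer that therapy's effect without ketamine is lost. It is not: Tables 4 to 6 show all four cells, and an unadjusted interaction and interval can be worked out from them. What is missing is a prespecified, site-adjusted estimate with its interval, and a statement of which result bears on enhancement.

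**The estimate would say little.** At ±37 to ±53 points that is fair, and limiting contrasts in a proof-of-concept trial is defensible. But the plan already reports other unpowered contrasts with intervals and no p-values, and a wide interval would correctly show that the question stays open. The exclusion of subgroup analyses is no bar, since both factors are randomised.

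**Contrast (a) is sound.** A reader might infer that pooling over therapy biases the ketamine estimate. The documents do not support that. It is a standard factorial margin under equal allocation, the drop-out allowance is described as conservative and applied equally to every cell, and nothing predicts opposite retention patterns by drug. SAP 6.5 also plans multiple imputation for the primary outcomes when more than 5% are missing. What remains is a modest safeguard for a primary analysis that stays complete-case.

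**Conclusion.** The point holds as a mismatch between a stated question and the planned estimates. No planned contrast estimates the drug-by-therapy interaction, and contrast (b) cannot separate enhancement from ordinary therapy benefit: two scenarios with the documents' margins give the same (a) and (b) but ratios of therapy relative risks of 1.00 and 0.67. It is not an error of sample size, and not a flaw in the answer to secondary objective 2.

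The interaction can be estimated but not usefully tested. The ±37 and ±53 points rest on assumed relapse of 25% in both ketamine cells and 50% in both placebo cells. The shifts of 3.3 and 6.7 points in (a) are hypothetical; they require a 20-point therapy effect and opposite retention patterns by drug. They justify adding a covariate, not a claim that the ketamine estimate is confounded.

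**What to change.** In SAP 4.5, 6.2 and 6.3, and in Tables 4 to 6:

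1. Add one exploratory drug-by-therapy interaction for each primary outcome, with a 95% interval and no p-value. For relapse, use the ratio of the two therapy relative risks (ketamine over placebo), with the risk-difference version alongside because the scales can disagree. For percentage days abstinent, use (K+PT − K+PE) − (P+PT − P+PE) on the means.
2. State that any conclusion about ketamine enhancing therapy rests on this estimate and not on (b) or (c), and that it is expected to be imprecise, with the widths given above.
3. Fit the ketamine versus placebo comparison with drug, therapy and site terms. This follows the factorial design and guards against chance or differential imbalance among completers.

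The cost is a few sentences in the SAP, one extra column in each of three tables, and a wide interval that has to be reported as such.

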**Risks / Benefits**

Excellent safety and tolerability data suggest that the risks of ketamine treatment would be low. Ketamine is currently indicated as an anaesthetic agent for diagnostic and surgical procedures. The use of ketamine for this anaesthetic purpose administers much higher doses (1 mg/kg to 4.5 mg/kg over 60 seconds) than our proposed dose of 0.8 mg/kg over 40 minutes, and even at these higher doses ketamine has a very good safety profile [34]. Use of ketamine is indicated with caution in the chronic alcoholic and the acutely alcohol-intoxicated patient. This is because ketamine is metabolised in the liver and hepatic clearance is required for termination of clinical effects. A prolonged duration of action may occur in patients with cirrhosis or other types of liver impairment. For this reason exclusion criteria will be liver function tests (LFTs, specifically bilirubin, ALT, AST) 3 times > the upper limit of normal. These are the same criteria used in the clinical trial for ketamine for depression in alcoholism in the US [31] by our collaborator at Yale. Her current study, and previous work which has administered ketamine to the same population (recently detoxified alcoholics) has shown good tolerability and safety in this group at a similar dose (0.5mg/kg IV over 40 minutes) [35; 36]. Further, breathalyser readings taken at infusion visits will be used to ensure that the visit is terminated where patients are currently intoxicated with alcohol.

The SPC states that dose reductions should be considered in alcoholic patients: our study does intend to use less than the minimum clinical dose of 1mg/kg. The SPC also states that abnormal liver function tests associated with ketamine use have been reported, particularly with extended use (>3 days) or drug abuse. Ketamine will be used at a lower dose than anaesthetic levels and will only be given in 3 isolated low doses, spaced at weekly intervals. Ketamine has a very short half-life and so will be quickly eliminated from the system. Benefits of no longer being dependent on alcohol for end-users are considerable and wide-ranging. Physical health would improve, and risks of alcohol-related diseases such as cirrhosis of the liver would decrease. Benefits would also be observed in terms of end users' mental health (depression, anxiety) and improved cognitive function, as well as quality of life. Benefits would be reflected economically, not only in a reduction in burden to the NHS but in more frequent and regular engagement in work activities, and a reduction in

crime. Alcohol is also associated with considerable acute harms. In 2012, 15,401 deaths in England and 1.24 million hospital admissions are attributable to alcohol consumption [41], therefore benefits would also accrue in a reduction in burden on the NHS and its workforce, in alcohol-related deaths and in other non-fatal acute harms. Importantly for end users, the brief nature of our pharmacological intervention will be less stigmatising than current treatments that require taking pharmacotherapies for prolonged periods. Data therefore suggest that the potential benefits to this group of patients far outweigh the risks.

## 2.5 Assessment and management of risk

This trial is categorised as TYPE B suggesting that the risk is somewhat higher than the risk of standard medical care. The IMP is licenced in the EU but is being trialled in a new indication

The table below summarises the risks, frequencies and mitigations of the IMP:

Potential risk	Risk Frequency *	Risk Management
Elevation of blood pressure, respiratory and heart rate	Common	
IMP will be administered at site. Vital signs will be monitored throughout the infusion of ketamine. Patients will not leave the site until they are judged 'street ready' by an anaesthetist, all signs of acute intoxication are absent and they will be advised to be collected by a responsible adult or transportation will be arranged for them. At discharge patients will be given a 24 hour contact card for emergencies.
 
Patients with uncontrolled hypertension, eclampsia or pre-eclampsia, severe coronary or myocardial disease, cerebrovascular accident or cerebral trauma will be excluded from the study (see section 5.2).
 
Patients taking thyroid hormones have an increased risk of developing hypertension and tachycardia when given with ketamine and therefore we will exclude these patients (see section 5.2).

Bradycardia, Arrhythmia,	Uncommon	IMP will be administered at site. Vital signs (heart rate, blood pressure, pulse oximetry)

Hypotension		
will be monitored throughout the infusion of ketamine. Patients will not leave the site until they are judged 'street ready' by an anaesthetist, all signs of acute intoxication are absent and they will be advised to be collected by a responsible adult or transportation will be arranged for them. At discharge patients will be given a 24 hour contact card for emergencies.
 
Patients with uncontrolled hypertension, eclampsia or pre-eclampsia, severe coronary or myocardial disease, cerebrovascular accident or cerebral trauma will be excluded from the study (see section 5.2).
 
Concomitant use of antihypertensive agents increases risk of hypotension and therefore, patients on antihypertensive agents will be excluded from the study (see section 5.2).

Anaphylactic reaction	Rare	
Ketamine will be administered by an anaesthetic registrar or consultant in the Clinical Research Facility at sites with access to resuscitative equipment. Patients will not leave the site until they are judged 'street ready' by an anaesthetist, all signs of acute intoxication are absent and they will be advised to be collected by a responsible adult or transportation will be arranged for them. At discharge patients will be given a 24 hour contact card for emergencies.
 
Patients with a known allergy to the IMP, placebo or any of its excipients will be excluded from the study (see section 5.2).
 
Patients on trial treatment phase who have an allergic reaction to ketamine will be withdrawn from further IMP treatment.

Elevated Intraocular pressure	Not known	
Patients with glaucoma or globe injuries will be excluded from the study (see section 5.2).

Diplopia	Common	
Patients will agree not to drive or operate heavy machinery on the day of the infusions. They will not leave the site until they are judged 'street ready' by an anaesthetist, all signs of acute intoxication are absent and they will be advised to be collected by a responsible adult or

		transportation will be arranged for them. At discharge patients will be given a 24 hour contact card for emergencies.
Nystagmus, Hypertonia, Tonic clonic movements	Common	These effects are reported with anaesthetic doses but the dose we are using in this trial is much lower than anaesthetic doses and over a much longer period. Whilst in previous studies we have observed nystagmus, we have not observed tonic clonic movements. To mitigate this unlikely risk patients will agree not to drive or operate heavy machinery on the day of the infusions. Patients will not leave the site until they are judged 'street ready' by an anaesthetist, all signs of acute intoxication are absent and they will be advised to be collected by a responsible adult or transportation will be arranged for them. At discharge patients will be given a 24 hour contact card for emergencies.
Prolonged acute effects, impaired hepatic clearance, drug-induced liver damage	Not known	
Use of ketamine is indicated with caution in the chronic alcoholic and the acutely alcohol-intoxicated patient. This is because ketamine is metabolised in the liver and hepatic clearance is required for termination of clinical effects. A prolonged duration of action may occur in patients with cirrhosis or other types of liver impairment.
 
Ketamine will be used at a lower dose than anaesthetic levels and will only be given in 3 isolated low doses, spaced at weekly intervals. Ketamine has a very short half-life and so will be quickly eliminated from the system.
 
Long term ketamine abuse can result in liver damage. However, we are giving just three, small doses. So liver damage is not an expected outcome.
 
Patients with liver function tests (LFTs, specifically bilirubin, ALT, AST) 3 times > the upper limit of normal will be excluded from the study (see section 5.2).

Emergence reactions: Hallucinations, abnormal dreams,	Common	Psychotomimetic symptoms or 'emergence reactions' are a key feature of ketamine administration. The psychological effects of anaesthetic doses vary between pleasant dream like states and vivid imagery to out of

nightmare, confusion, agitation, abnormal behaviour
		
body experiences and hallucinations. A review examining these phenomena across 450 volunteers given similar doses to those to be given in this study found only 6 incidences of such mental states that were unpleasant enough to require the infusion to be stopped, all of which remitted completely in the hours following the cessation of the infusion [20]. Patients with schizophrenia given doses of ketamine similar to those administered in this study have been known to have longer lasting psychotomimetic states [38] and for that reason psychosis in the patient and schizophrenia in the patient or a first degree relative are an exclusion criteria for the study (see section 5.2). Emergence phenomena can be reduced in anaesthesia with the co-administration of a benzodiazepine; midazolam can be administered by the anaesthetist if the emergence phenomena are intolerable to the patient. Alternatively the infusion can be stopped and, due to short half-life of ketamine, these effects should remit very rapidly.


Delirium, Flashback, dysphoria, insomnia, disorientation
	
Rare
	
This dose is lower than an anaesthetic dose, where risks are rare. A review examining these phenomena across 450 volunteers given similar doses to those to be given in this study found only 6 incidences of such mental states that were unpleasant enough to require the infusion to be stopped, all of which remitted completely in the hours following the cessation of the infusion [20]. Patients with schizophrenia given doses of ketamine similar to those administered in this study have been known to have longer lasting psychotomimetic states [38] and for that reason psychosis in the patient and schizophrenia in the patient or a first degree relative are an exclusion criteria for the study (see section 5.2). Emergence phenomena can be reduced in anaesthesia with the co-administration of a benzodiazepine; midazolam can be administered by the anaesthetist any symptoms are intolerable to the patient. Alternatively the infusion can be stopped and, due to short half-life of ketamine, these

		
effects should remit very rapidly.
 
IMP will be administered at site. Patients will not leave the site until they are judged 'street ready' by an anaesthetist, all signs of acute intoxication are absent and they will be advised to be collected by a responsible adult or transportation will be arranged for them. At discharge patients will be given a 24 hour contact card for emergencies.

Anxiety	Uncommon	If patients find any symptoms intolerable, a benzodiazepine can be co-administered which should reduce anxiety. Alternatively the infusion can be stopped and, due to short half-life of ketamine, these effects should remit very rapidly.
Nausea, Vomiting	Common	Patients will fast for 6 hours before the infusion to reduce the risk of vomiting and pulmonary aspiration. In the case of vomiting, or if nausea is intolerable to the patient then the infusion will be stopped, whereupon these symptoms should remit very quickly.
Ketamine abuse	Not known	Patients with a significant history of substance misuse other than alcohol will be excluded. No previous studies giving ketamine to this patient group found evidence that they subsequently went on to abuse the drug [4; 5].
Respiratory depression, laryngospasm, obstructive airway disorder or apnoea	Rare	These effects occur only with large doses and rapid infusions. Ketamine will be administered at a sub-anaesthetic dose and infused over 40 minutes, in the numerous previous studies using this dosing regimen this adverse effect has never been reported.
Salivary hypersecretion	Rare	Participants will be warned of this potential side effect, which would not be prolonged and for the duration of the infusion only. Increased salivation in this context should not be associated with any further risks. We have not observed this adverse event with our previous sub-anaesthetic ketamine studies, therefore it may be confined to anaesthetic doses, but should there be any increased salivation this will be for the duration of the infusion only.
Erythema,	Common	Mild rash and redness of the skin have been

Rash morbilliform		observed following ketamine, which remit upon cessation of administration of the drug, however these might concern participants if unexpected, therefore we will fully inform participants of this possibility in the information sheet.
Cystitis, Haemorrhagic cystitis	Rare	Ketamine-induced ulcerative cystitis is now a clinical condition observed after prolonged daily or more than daily use of ketamine in abusers. Only one case has been reported in the medical literature following the repeated daily administration of ketamine for chronic pain. As patients in this study will only receive 3 doses of ketamine, spaced at a week apart, we do not anticipate cystitis to be a risk from ketamine administration in the current study, however this will be carefully monitored and we shall ask questions pertaining to cystitis in our recording of adverse events.
Injection site pain, injection site rash	Uncommon	If participants experience this uncommon side effect, local anaesthetic may be given. They will be informed of the potential of a rash and this will be carefully monitored.
Assessment of psychiatric conditions	Inclusion of a participant with a comorbid psychiatric disorder	The SPC for ketamine advises caution in patients with a history of psychosis therefore all participants will be assessed for psychosis using the SCID. For other comorbid psychiatric disorders the research team will ask the participant's medical health professional to notify us. Hence anyone with a current psychiatric disorder apart from depression and anxiety will be excluded.
Urine drug screen	Allowing a cannabis dependent participant to take part in the trial.	People with a previous or current cannabis dependence/severe use disorder diagnosis will be excluded from the trial, as will people with any other substance dependence/severe use disorder diagnosis (apart from alcohol). Therefore, the risk of including a cannabis dependent participant will be minimal. However, occasional cannabis use is comorbid with alcohol use. Cannabis use, like other substance use, will be monitored throughout the trial using a urine drug screen. Cannabis consumption leads to THC remaining in urine for approximately 28 days. Therefore,

		occasional use of cannabis may result in a positive THC urine screen. However, occasional cannabis use is not grounds for exclusion. Therefore, people who are not dependent on cannabis (and do not have a history of it), but do have a positive THC urine drug screen, may be included.
Urine drug screen	Allowing a benzodiazepine dependent participant to take part in the trial.	People with a diagnosis of previous or current benzodiazepine dependence/severe use disorder will be excluded from the trial, as will people with a diagnosis of any other substance dependence/severe use disorder (apart from alcohol). Therefore, the risk of including a benzodiazepine dependent participant is minimal. However, benzodiazepines are used in community and inpatient alcohol detox and for sleep problems. Benzodiazepine use, like other substance use, will be monitored throughout the trial using a urine drug screen. Benzodiazepine use has a relatively long detection window (up to 7 days for long-acting). Therefore, benzodiazepine use in detox may result in a positive benzodiazepine urine screen. However use of benzodiazepines in detox is not grounds for exclusion. Therefore, people who are not dependent on benzodiazepines (and do not have a history of it), but do have a positive benzodiazepine urine drug screen, may be included.

\* From SPC of anaesthetic use of ketamine (Appendix E)

